5.2 RISKS OF INVESTIGATIONAL PRODUCT OR INTERVENTION CITED IN MEDICAL LITERATURE

5.2.1 SLIT: GRAZAX® AND GRAZAX® PLACEBO

See Section 1.2.1 for additional details of risk cited in the medical literature.

5.2.2 DUPILUMAB: DUPIXENT® AND DUPIXENT® PLACEBO

See Section 1.2.2 for details of risks cited in medical literature and the package insert.

5.2.3 COMBINATION THERAPY

There is no available data concerning the concurrent administration of Grazax® and Dupixent® in man. Both agents are well-tolerated with a defined profile of generally mild AEs, in particular mild-moderate, largely self-resolving reactions at the site of local administration for both products and the occurrence of mild-moderate conjunctivitis for Dupixent®, so far largely confined to participants with atopic eczema. The mechanism of action of Dupixent® is such that it is anticipated that the local allergy-related side-effects of sublingual Grazax® will likely be ameliorated by Dupixent®.

Grazax® will be administered sublingually daily and Dupixent® will be administered by subcutaneous injection every 2 weeks. On the day that Dupixent® is administered, this will be separated from Grazax® by a minimum interval of 6 hours. This duration was chosen because any reactions to Grazax® occur within 1 hour thereby allowing for attribution of any AEs to the appropriate study therapy.

5.3 RISKS OF OTHER PROTOCOL SPECIFIED MEDICATIONS

Besides Dupixent® and Grazax®, other protocol specified medications would include oral/ocular antihistamines; oral, nasal, and inhaled corticosteroids; and combination inhaled long-acting beta agonists with corticosteroids. Ocular antihistamines may rarely be associated with local irritation. Oral antihistamines may be associated with drowsiness. Nasal steroids may be associated with local irritation, sneezing, and rhinorrhea. Minor nasal bleeding may also occur. Inhaled corticosteroids may be associated with cough, hoarseness, and oral candidiasis. Rarely, systemic absorption of inhaled corticosteroids may lead to the side effects listed below under oral corticosteroids. Inhaled beta agonists may be associated tachycardia, palpitations, tremor, headache, hypokalemia, and elevations in serum glucose. Oral steroids when used continuously for prolonged periods of time (>2 weeks) may be associated with adrenal insufficiency, skin atrophy, osteoporosis, hypertension, diabetes, glaucoma, cataracts, dyspepsia and mood changes. However, in this trial, only short courses (up to 7 days) of oral corticosteroids will be dispensed and only after consultation with the study clinician and monitoring. Very few participants are likely to require systemic corticosteroids as rescue medication.

5.4 RISKS OF STUDY PROCEDURES

5.4.1 INTRADERMAL AND SKIN PRICK TESTS

Participants may experience mild to moderate pruritus and local swelling at the sites of skin pricks with allergen and the positive control (histamine dihydrochloride 10mg/ml). They may experience larger swellings and mild discomfort following intradermal testing. The symptoms are not bothersome and treatment with oral antihistamines is effective although almost never required. Although rare, theoretical risks do include systemic reactions, including anaphylaxis, after intradermal skin tests with standardized aeroallergen extracts.⁶⁰ A physician will always be present and drugs and equipment for treatment of anaphylactic reactions, including epinephrine drawn up in a syringe, will always be available.

5.4.2 NASAL ALLERGEN CHALLENGE (NAC)

The NAC will be performed using grass pollen extract (*Phleum pratense*) (ALK-Abelló). Application of the allergen to the nasal mucosa is undertaken using a disposable nasal pump spray (Bidose®; Aptar Pharma, France). Nasal challenge provokes immediate symptoms at 0-1 hour after challenge followed by milder delayed-in-time late responses at 1-10 hours (generally mild and not captured in this study). The participant will experience typical hay fever symptoms including nasal itching, nasal blockage, sneezing, nasal watery discharge, itchy eyes, watery eyes, and redness of the conjunctivae. If bothersome nasal and/or ocular symptoms persist after the period of 0-1 hour observation in the clinical unit, participants will be offered treatment with oral antihistamines. Unless bothersome symptoms persist, the participants will be discharged after one hour and provided with a telephone contact number with immediate access for 24 hours after challenge.

There is a remote risk of provoking mild asthma symptoms after a NAC. All participants' peak expiratory flow (PEF) will be recorded before and after nasal challenge. Inhaled bronchodilators and corticosteroids will be immediately available for treatment. As for any intervention with allergen to which an individual is sensitive, there is the theoretical risk of developing a systemic allergic/anaphylactic reaction, although this has never been observed in studies of several hundred participants over the past 30 years in the Section for Allergy and Clinical Immunology at NHLI, Imperial College. Nevertheless, a trained physician and injectable adrenaline, oxygen and intravenous equipment and fluids will be immediately available in the clinical unit during participants' NAC visits.

5.4.3 NASAL LAVAGE

Prior to nasal challenge, a saline nasal lavage will be performed with a commercially available preparation (Sinus Rinse®, NeilMed Pharmaceuticals) diluted in 240ml (8 oz.) of warm distilled water. This is a non-irritant, preservative free, pH neutral solution that contains sodium chloride, sodium bicarbonate, and iodine. Sinus Rinse® is widely available and no adverse effects are expected.

5.4.4 NASAL FLUID COLLECTION

Nasal fluid will be collected on 1 cm polycarbonate sponges that are inserted into the nostril using fine forceps, placed adjacent to the inferior turbinate, and left *in situ* for exactly 2 minutes before retrieval. Risks include slight discomfort and reflex eye watering.

5.4.5 NASAL BRUSHINGS

Cells from the nasal epithelium will be collected by nasal brushing. Risks include local burning with eye watering and rarely slight local bleeding. The symptoms resolve within minutes.

5.4.6 VENIPUNCTURE

Blood will be drawn from an antecubital vein using a 19 gauge butterfly (or similar) sterile cannula. Participants may experience some minor discomfort on skin puncture during insertion of the cannula. Blood samples will be taken with the participant sitting down. If they experience faintness or frank vaso-vagal syncope due to venipuncture, they will be assisted to lie flat and blood pressure and vital signs will be monitored until symptoms resolve. Oxygen and intravenous fluids will be available in the exceptionally unlikely event that they are required.

5.5 POTENTIAL BENEFITS

There is no assurance of therapeutic benefit from participation. Based on previous studies, it is likely that participants who are randomly assigned to receive immunotherapy with Grazax[®] will have an improvement in allergic rhinitis symptoms.¹³ Given the randomization scheme described in Section 3.1, we estimate that at least 2/3 of participants will receive Grazax[®] and may receive some benefit from this study. The impact of dupilumab, however, is unknown. Some participants will not receive either immunotherapy with Grazax[®] or dupilumab; however, all participants in the study will have access to approved rescue medications. Participants with co-morbid atopic dermatitis and/or asthma may benefit from administration of dupilumab.

6. INVESTIGATIONAL AGENTS

6.1 CHARACTERISTICS OF INVESTIGATIONAL AGENTS

6.1.1 SLIT: GRAZAX[®] AND GRAZAX[®] PLACEBO

6.1.1.1 Name, Manufacturer, and Indication

Grazax[®] 75,000 SQ-T oral lyophilisate (Grazax[®], ALK- Abelló Horsholm, Denmark) is standardized allergen extract grass pollen from Timothy grass (*Phleum pratense*). It is in the form of a white to off-white circular oral lyophilisate tablet. Grazax[®] has been used extensively in clinical trials.^{13,25,38,39} The product characteristics are well described in a 2004 version of the Investigational Brochure and in the 2018 version of a SmPC.⁶⁰

6.1.1.2 Formulation, Packaging, and Labeling

SQ Standardized Grass Allergy Immunotherapy (Grazax[®], ALK- Abelló Horsholm, Denmark) is formulated as a freeze-dried oral lyophilisate/orally disintegrating tablet for oromucosal use. The active pharmaceutical ingredient is a standardized allergen extract derived from extraction and purification of grass pollen from Timothy grass (*Phleum pratense*). The biological activity of the allergen is expressed in standardized quality units. The recommended dosage is one oral lyophilisate (75,000 Standardized Quality Tablet units (SQ-T) or approximately 2800 bioequivalent allergy units (BAU), a measure of *Phleum pratense* SQ total biological potency defined by the FDA. This dose is equivalent to 15 µg of *Phleum pratense* 5. The non-active ingredients consist of fish gelatin, mannitol, sodium hydroxide and water.

Grazax[®] placebo is a tablet whose composition is identical to the active Grazax[®] tablet with the only exception being exclusion of the active pharmaceutical ingredient, *Phleum pratense* SQ. Grazax[®] and Grazax[®] placebo tablets will be supplied in blister packs by ALK-Abelló.

6.1.1.3 Dosage, Administration, and Storage

The first dose of Grazax[®] or Grazax[®] placebo tablet will be administered under investigator's supervision in the clinic. Participants will be observed for at least 60 minutes.

Home sublingual administration of Grazax[®] or Grazax[®] placebo tablets will occur daily during the first 2 years of the trial as specified in the Schedule of Events. Tablets should be removed from the blister packs with dry fingers and should be taken immediately after opening the blister. Each tablet should be placed underneath the tongue until fully dissolved (1–2 minutes). Swallowing should be avoided for about 1 minute. Food and beverage should not be consumed for the following 5 minutes. On days that participants receive dupilumab/placebo every two weeks, SLIT/placebo will be administered with a minimum interval of 6 hours. Study medication may be temporarily withheld at the investigator's discretion, for example due to illness of the participant.

The most recent SmPC can be found here:

<https://www.medicines.org.uk/emc/product/315>.

According to SmPC, Grazax[®] does not require any special storage conditions.⁶⁰

Special Warnings and Precautions for Use

In case of oral surgery, including dental extraction, treatment with Grazax[®] should be stopped for 7 days to allow healing of the oral cavity.

Grazax[®] tablets are sensitive to moisture and blister packs should be stored unopened until use. The current formulation has been shown to be stable when stored at room temperature in unopened blisters.

6.1.2 DUPILUMAB: DUPIXENT® AND DUPIXENT® PLACEBO

6.1.2.1 *Name, Manufacturer, and Indication*

Dupilumab is approved for marketing as Dupixent® by Sanofi in the European Union currently, including the UK and is indicated in the treatment of asthma and moderate to severe atopic dermatitis in adult patients.

6.1.2.2 *Formulation, Packaging, and Labeling*

Dupixent® has the following pharmaceutical form:

- Solution for injection (injection)
- Clear to slightly opalescent, colorless to pale yellow solution, which is free from visible particulates.

Each single-use pre-filled syringe contains 300 mg of dupilumab in a 2 ml (150 mg/ml) aqueous buffered solution, pH 5.9. Excipients include L-arginine hydrochloride, L-histidine, sodium acetate, sucrose, and polysorbate 80.

The placebo for Dupixent® will also be provided in pre-filled syringes. It will be identical in appearance to active Dupixent®. Excipients are identical between placebo and active Dupixent®.

Study specific labels will be applied. Dupixent® and matching placebo will be supplied by Regeneron.

6.1.2.3 *Dosage, Administration, and Storage*

We will use the recommended dose of dupilumab for adult patients: an initial dose of 600 mg (two 300 mg injections), followed by 300 mg given every two weeks administered as subcutaneous injection. Administration of dupilumab will occur at a minimum interval of six hours from a SLIT dose. Participants will be observed for 30 minutes after the first three dupilumab injections. A minimum of 7 days and a maximum of 24 days will occur between dupilumab doses. Study medication may be temporarily withheld at the investigator's discretion, for example due to illness of the participant.

Dupixent® should be stored in refrigerated condition between 2° C and 8° C.

The shelf-life of Dupixent® is 30 months at 2-8° C. Pre-filled syringes may be kept at room temperature (up to 25° C) for a maximum of 14 days (Section 6.1 of the SmPC).⁴⁷

The most recent SmPC can be found here:

<https://www.medicines.org.uk/emc/product/8553>.

6.2 DRUG ACCOUNTABILITY

An investigator is required to maintain adequate records of the disposition of the investigational product, including the date and quantity of drug that was received, the participants to whom drug was dispensed (participant by participant accounting), and an account of any drug accidentally or deliberately destroyed.

Records for receipt, storage, use, and disposition of the study drug will be maintained by the study site. A drug-dispensing log will be kept current for each participant and will contain the identification of each participant and the date and quantity of drug dispensed.

All records regarding disposition of the investigational product will be available for inspection by the clinical trial monitor.

6.3 ASSESSMENT OF PARTICIPANT COMPLIANCE WITH INVESTIGATIONAL AGENTS

Participants will be asked to return used Grazax[®] and Grazax[®] placebo blister packs and unused tablets at study visits every 4 weeks when they attend for alternate two weekly visits to receive dupilumab. Those participants with less than 75% compliance with study treatments will be counseled.

6.4 TOXICITY PREVENTION AND MANAGEMENT

6.4.1 TOXICITY PREVENTION

Participants will be counselled on the likelihood of local reactions and their usual short and self-limiting course. A 24-hour telephone link is available for participants to contact study clinicians if they have concerns. If bothersome, symptoms may be partially relieved by pre-treatment with a non-sedating oral anti-histamine (desloratidine) and/or ocular anti-histamine (olopatadine) which will be supplied if needed.

Participants will be monitored for both systemic and local side effects during study visits. There is no intention to modify the dose of either SLIT or dupilumab. SLIT should be withheld on days when there are any local inflammatory conditions or local bleeding in the mouth, for example from dental treatment. SLIT can be restarted thereafter with the same daily dose. Participants will be explicitly advised not to take more than one SLIT tablet daily – not for ‘catchup’ due to missed doses nor for any other reason.

6.4.2 TOXICITY MANAGEMENT

In the unlikely event that participants experience symptoms and signs of asthma, clinical features (PEF and oxygen saturation) will be assessed. Treatment will be initiated according to the severity of symptoms. Inhaled β_2 agonists will be given and if no response, nebulized β_2 agonist and ipratropium bromide driven by oxygen will be given and if needed, oral or intravenous corticosteroid will be given and maintained until recovery.

Cases of anaphylactic reactions have rarely been reported after Grazax[®]. The first dose of Grazax[®] is therefore given under medical supervision and participants observed for at least one hour after administration. In the extremely unlikely event that anaphylaxis occurs, participants will be treated with intramuscular adrenaline and oxygen followed by intravenous antihistamine and corticosteroid and observed for at least 4 hours after the event.

Given the increased incidence of conjunctivitis observed in the dupilumab trials in atopic dermatitis, conjunctivitis symptoms will be recorded if reported by participants.

Participants who volunteer bothersome eye symptoms that are not attributable to relevant allergen exposures will be referred for an eye assessment and examination by a consultant ophthalmologist affiliated with Royal Brompton Hospital/Imperial College London. The consulting ophthalmologist will be asked to assess whether there is conjunctival inflammation and offer an opinion as to whether this may be secondary to treatment as opposed to another cause.

6.5 PREMATURE DISCONTINUATION OF INVESTIGATIONAL AGENT

Study therapy may be prematurely discontinued for any participant for any of the reasons listed in Section 11.2.

Study therapy may also be prematurely discontinued for any participant if the investigator believes that the study treatment is no longer in the best interest of the participant.

Participants who discontinue or are discontinued from the use of study treatment will be invited to continue participating in the study and undergo evaluations per protocol for the remaining duration of the study.

7. OTHER MEDICATIONS

7.1 CONCOMITANT MEDICATIONS

Use of the following rescue medications is permitted. These medications are considered standard of care and will be provided by the study approximately 2 weeks before the start of the pollen season and throughout the pollen season:

- Antihistamine tablets (desloratidine)
- Nasal corticosteroid spray (fluticasone propionate aqueous nasal spray)
- Ophthalmic antihistamine drops (olopatadine)
- Short-acting beta2-agonist inhaler (albuterol)

Use of the following rescue medications will be provided only after participants are evaluated by a study clinician. Evaluations may occur by phone contact or clinic visit.

- Oral corticosteroid (prednisolone 5mg tablets)
- Corticosteroid inhaler (fluticasone propionate)
- Combination of long-acting beta-agonist and corticosteroid inhaler (salmeterol/fluticasone)

7.2 PROHIBITED MEDICATIONS

Use of the following medications is prohibited during study participation:

- Administration of live attenuated vaccines: live attenuated vaccines should not be given concurrently with dupilumab as clinical safety and efficacy has not been established (if needed, live vaccine should be administered to participants before commencement of dupilumab). These vaccines should not be given within 4 weeks of dupilumab or dupilumab placebo injection.
- Tricyclic antidepressants
- Monoamine oxidase inhibitors
- Anti-IgE, anti-IL-5, anti-IL-5 receptor, other monoclonal antibodies targeting the human immune system, or any other biologic therapies. Antiviral monoclonal antibodies are permitted.
- Refer to Appendix 7 for required medication washout periods prior to the NAC and skin prick testing

8. STUDY PROCEDURES / ASSESSMENTS

8.1 ENROLLMENT

The research study will be explained by a study clinician in lay terms to each potential research participant. The potential participant will sign and date an informed consent form that is countersigned at the same time by the study clinician before undergoing any study procedures.

8.2 SCREENING/BASELINE VISIT

The Schedules of Events for this trial are represented in [Appendices 1-5](#). The timing of the screening visit is determined by whether the participant's first visit falls in or out of season (See Section 8.5).

8.3 STUDY VISITS OR STUDY ASSESSMENTS

8.3.1 GENERAL ASSESSMENTS

- Informed consent: Written informed consent will be obtained before any study assessments or procedures are performed.
- Eligibility criteria: Eligibility for study participation will be assessed during the screening period.
- Demographics: age and ethnicity.
- Medical history: A history will be taken to determine if the participant has had any clinically significant diseases or medical procedures other than the disease under study.
- Allergy history.
- Rhinoconjunctivitis severity screening evaluation (ARIA severity score).

- Directed physical examination: includes body systems: respiratory, cardiovascular, skin, and conjunctivae.
- Vital signs: blood pressure, temperature, pulse, and respiratory rate.
- Pulmonary Function Test (Spirometry, record one-second FEV₁ and forced vital capacity).
- AEs: Participants will be assessed at every visit for AEs. Prior to home administration of Dupixent or Dupixent placebo, participants will be asked whether there have been any AEs. If they report Yes, the study team will assess the changes before they proceed with the injection.
- Concomitant medications: All concomitant medications and their indications will be recorded at every visit. Prior to home administration of Dupixent or Dupixent placebo, participants will be asked whether there have been any changes in Concomitant medications. If they report Yes, the study team will assess the changes before they proceed with the injection.

8.3.2 LOCAL LABORATORY ASSESSMENTS

- Serum pregnancy test
- Urine pregnancy test (monthly)
- Hematology: Complete blood count with differential
- Comprehensive chemistry: albumin, bilirubin total, creatinine, glucose, potassium, protein total, sodium, alanine amino transferase (ALT or SGPT), Alkaline Phosphatase (ALP), urea.
- Total IgE and specific IgE to grass pollen (*Phleum pratense*) and birch pollen

8.3.3 CLINICAL ASSESSMENTS

Clinical allergy assessments comprise NACs and several forms of skin testing and provide eligibility information, clinical characterization and allergy status. It is important that prior to all such assessments, participants avoid medications that might unduly modify allergic responses independent of the study interventions. Certain procedures may generate aerosols and will be conducted only if they comply with local hospital guidelines at the time of the procedure. Washout periods for specific medications are shown in Appendix 7.

Potential aerosol generating procedures

- Nasal Allergen Challenge
- Visual Analogue Scale (Appendix 9)
- Peak expiratory flow testing
- Peak nasal inspiratory flow testing
- Pulmonary Function Testing (Spirometry, FEV₁)

Non-aerosol generating procedures

- Skin prick test endpoint titration – *Phleum pratense*
- Intradermal skin test – *Phleum pratense*
- Skin prick test panel: Timothy grass pollen (*Phleum pratense*), silver birch (*Betula verrucosa*), mugwort (*Artemisia vulgaris*), house dust mite (*Dermatophagoides pteronyssinus*), cat hair (*Felis domesticus*), dog hair (*Canis familiaris*), *Aspergillus fumigatus*, *Cladosporium herbarum*, *Alternaria alternata*, negative control, and positive control (*histamine dihydrochloride*)

8.3.4 RHINITIS ASSESSMENTS

Participants may be asked to utilize a 21 CFR Part 11 compliant mobile application to submit this information.

- Weekly MiniRQLQ (Appendix 10) during pollen season
- Global Evaluation No. 1 (Appendix 12) after pollen season
- Global Evaluation No. 2 (Appendix 12) after pollen season
- Weekly CSMS during pollen season (Appendix 11)
- MRSUI (Appendix 13) in and out of pollen season

8.3.5 MECHANISTIC ASSESSMENTS

See Section 9 for detailed discussion of mechanistic assays.

8.4 UNSCHEDULED VISITS

Unscheduled visits may be performed in the event that participants experience an AE requiring medical attention, a disease exacerbation requiring treatment or because the participant prematurely terminates from the study (see Section 11.2).

8.5 VISIT WINDOWS

All scheduled study visits will aim to occur within the time limits specified below and may be adjusted based on pollen count and participant availability.

Table 7. Visit Windows all Participants (See Appendices 1-5)

Visit	Visit description	Visit Window
Visit -4	Screening	October 2020 to January 2022
Visit -3	Rescue medication dispensing visit	April 1 to July 31
Visit -2	Baseline In-season assessments	June 1 to July 31
Visit -1	Baseline NAC	September to January
Visit 0	Randomization – 1 st dupilumab/dupilumab placebo dose	≥ 28 days after Visit -1 and before end of February
Visit 1	1 st SLIT/SLIT placebo dose	≥12 hours from Visit 0 and ≥ 7 days prior to Visit 2.
Visits 2-53	Treatment visits	Every 2 weeks from Visit 0 through week 104 +/- 10 days (with at least 7 days between treatment visits)
Visits 54-65	Observation visits	Every 4 weeks from 108 to 156 +/- 14 days
S1	Out of season visit assessment year 1	January to April
S2, S7, S12	Pre-season visit	April to May
S3, S8, S13	In-season visits	May to August
S4, S9, S14	Out-of-season NAC visits	September to January 1, 2 and 3 calendar years after Visit -1 +/- 14 days
S5, S10, S15	Mechanistic draws post NAC visits	≥ 4 weeks post NAC visit (S4, S9, S14) and before end of February each year
S6, S11	Out of Season visit	January to April

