3. STUDY DESIGN

3.1 DESCRIPTION OF THE STUDY DESIGN

This is a randomized, double blinded trial in adults (n=108) with moderate to severe seasonal allergic rhinitis with allergic sensitization to grass pollen.

During the screening visit, participants will be asked for demographic information, complete a brief questionnaire concerning their allergic rhinitis, severity and duration, and impact on their quality of life, work or school performance and sleep. Any co-morbidities including asthma, eczema, or sinusitis; their past medical history; smoking history and medication history will be recorded. Participants will undergo skin prick testing with a panel of inhaled aeroallergens and with positive and negative controls. A blood sample will be taken for full blood count, total and specific IgE to grass and tree pollen, comprehensive chemistry and liver function tests.

[figure not shown]
Participants who meet eligibility criteria and choose to enroll will undergo a baseline visit. Thereafter participants will be randomized 1:1:1 to three parallel treatment arms as follows:

- Combination of SLIT and dupilumab (n=36)
- SLIT plus dupilumab placebo (n=36)
- SLIT placebo plus dupilumab placebo (i.e. double-placebo) (n=36)

Grazax[®] is a sublingual grass immunotherapy product approved for clinical use in the United Kingdom and will be used as SLIT in this study. It (and its matching placebo) will be self-administered daily by participants through week 104. Dupixent[®] is the brand name for dupilumab and is a monoclonal antibody against the IL-4 receptor. Dupilumab and its placebo will be administered every two weeks by subcutaneous injection through week 104. With appropriate training by study personnel, alternate doses of dupilumab (and other occasional doses as required) may be self-administered by participants at home. Dupilumab is approved for self-administration by patients. The treatment phase of 104 weeks will be followed by an observation phase of 52 weeks.

[figure not shown]
A NAC will be performed at baseline (Visit -1) and repeated annually after 1 and 2 years of study treatment and at 3 years (1 year after completion of study treatment). Annual NACs should be done at the same time every year, within +/-14 days of the preceding year's NAC. Blood, nasal brushings, and nasal fluid samples will be collected as outlined in Appendices 1 through 5.

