3.2 PRIMARY ENDPOINT

NAC (TNSS Area-under-Curve [AUC_{0-1hr}]) at year 3, one year after completion of treatment. The primary comparison will be between the combination of SLIT and dupilumab arm and the double-placebo arms (clinical tolerance endpoint).

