3.3 SECONDARY ENDPOINTS

Clinical tolerance endpoints at year 3, one year after completion of study treatment. The comparison will be between the combination of SLIT and dupilumab and the double-placebo arms.

1. Peak nasal inspiratory flow (Delta PNIF AUC_{0-1hr})
2. Size of early and late intradermal skin test response
3. Size of the skin prick test endpoint titration response
4. Seasonal outcomes
 - a. Weekly seasonal symptoms (Visual Analogue Scale [VAS] 0-10 cms) and combined symptom medication scores (CSMS)
 - b. Weekly rhinitis quality of life scores (Juniper mini-Rhinoconjunctivitis Quality of Life Questionnaire [miniRQLQ]) measured in-season
 - c. Modified Rhinitis Symptom Utility Index (MRSUI) measured in-season and out-of-season
 - d. Global Evaluations No. 1 and No. 2 after the season

Clinical desensitization endpoints at year 1 and 2 whilst on study treatment. The comparison will be between the combination of SLIT and dupilumab and the double-placebo arms.

5. TNSS AUC_{0-1hr}
6. Delta PNIF AUC_{0-1hr}
7. Size of early and late intradermal skin test response
8. Size of skin prick test endpoint titration response
9. Seasonal outcomes
 - a. Weekly seasonal symptoms (VAS 0-10 cms) and CSMS
 - b. Weekly rhinitis quality of life scores miniRQLQ measured in-season
 - c. MRSUI measured in-season and out-of-season
 - d. Global Evaluations No. 1 and No. 2 after the season

Safety Endpoints

10. The number, severity, and relatedness of local and systemic AEs and SAEs reported during screening, at baseline, during years 1 and 2 whilst on study treatment, and during year 3 (one year after completion of study treatment). Each treatment arm will be summarized separately.

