9. ENDPOINT EVALUATION

9.1. Primary Endpoint

The primary endpoint is the NAC TNSS AUC_{0-1hr} at year 3, one year after completion of treatment.

[figure not shown]

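### The year-3 nasal challenge is scheduled from the baseline challenge, not the last dose, so it falls nominally 27 to 49 weeks off treatment rather than the stated one year

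*Protocol*

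**What the plan says.** **The endpoint definition.** Protocol Section 3.2 places the primary NAC "at year 3, one year after completion of treatment". Section 3.1 describes the final challenge as "at 3 years (1 year after completion of study treatment", and says that the earlier ones come after 1 and 2 years of study treatment. It also gives a 52-week observation phase after the 104-week treatment phase. Section 3.3 heads the secondary list "Clinical tolerance endpoints at year 3, one year after completion of study treatment". SAP Section 9.1 agrees: "The primary endpoint is the NAC TNSS AUC_{0-1hr} at year 3, one year after completion of treatment".

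**The schedule.** Protocol Section 8.5, Table 7, sets these windows:

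- Baseline NAC (Visit -1): "September to January".
- Randomisation and first injection (Visit 0): "≥ 28 days after Visit -1 and before end of February".
- Treatment visits: "Every 2 weeks from Visit 0 through week 104 +/- 10 days (with at least 7 days between treatment visits".
- Annual NACs (S4, S9, S14): "September to January 1, 2 and 3 calendar years after Visit -1 +/- 14 days".

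A footnote to Appendix 5 also ties the annual NAC to the calendar date of the baseline NAC, within 14 days, so that it is done at the same time each year. Section 3.1 uses another anchor, within 14 days of the preceding year's NAC. No window ties S14 to the last dose.

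**The analysis.** The SAP's primary estimand (Section 5) and model (Section 9.1.2) refer to year 3 as a category. SAP Section 10.2 plans no exposure summary beyond compliance. SAP Section 6.1 lists dosing and visit dates but plans no summary of time off treatment.

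**The concern.** Two clocks are in use. Treatment runs from Visit 0, while the annual challenges run from Visit -1, at least 28 days earlier. Every day between the two comes off the off-treatment interval at S14. The definition promises a fixed one-year interval, and the schedule gives a shorter one that varies between participants.

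The length of that interval matters because the trial asks whether an effect persists after treatment stops. Protocol Section 1.2 supplies the precedent: in the GRASS trial a reduction of about 30% during treatment (TNSS AUC over 0 to 10 hours) fell to 7% after withdrawal. Evidence of persistence at about 27 weeks is weaker than evidence at 52 weeks, and a reader relying on the endpoint definition would assume the latter. The same anchor also shifts the challenges labelled year 1 and year 2, which the SAP uses for desensitisation and for an exploratory year-3 versus year-2 comparison (SAP Section 9.2.1).

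**Working it through.** **Inputs** (Table 7 unless noted)

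- Visit -1: 1 September 2021 to 31 January 2022. This is the autumn after the 2021 baseline season, and Appendix 5 puts the first on-study visits in 2022.
- Gap from Visit -1 to Visit 0: at least 28 days. The longest is 1 September 2021 to 28 February 2022, which is 180 days.
- Treatment: 104 × 7 = 728 days from Visit 0, with a tolerance of 10 days.
- S14: 3 calendar years after Visit -1. This is 1,096 days, because 29 February 2024 lies inside the span. The tolerance is 14 days.

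**Stated figure.** Days off treatment at S14 = 1,096 − (gap + 728) = 368 − gap. An interval of 365 days needs a gap of 3 days, but the minimum is 28. The stated year does not reproduce.

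**Nominal interval to S14**

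| Gap | First dose | Week 104 | S14 | Days off | Weeks off |
|---|---|---|---|---|---|
| 28 days | 29 Sep 2021 | 27 Sep 2023 | 1 Sep 2024 | 368 − 28 = 340 | 48.6 |
| 180 days | 28 Feb 2022 | 26 Feb 2024 | 1 Sep 2024 | 368 − 180 = 188 | 26.9 |

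The spread is 340 − 188 = 152 days, or 21.7 weeks. Weighting every permitted date pair equally, which is an assumption, gives a mean of about 41 weeks.

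**With tolerances**

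- Longest: 340 + 14 + 10 = 364 days (52.0 weeks).
- Shortest: 188 − 14 − 10 = 164 days (23.4 weeks). If S14 must stay within September to January, it is 178 days (25.4 weeks).
- Enumerating all permitted dates, none reaches 365 days.

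**Section 3.1 anchor.** Tolerances of 14 days can accumulate over three years to 42 days, so the longest interval is 340 + 42 + 10 = 392 days (56.0 weeks). About 3% of enumerated combinations reach 365 days. That is a share of date combinations, not a forecast for participants.

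**Year-3 season.** SAP Section 9.2.6 collects ten weeks of scores from about the end of May to the end of July 2024.

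- Latest last dose, 26 February 2024, to 27 May 2024: 91 days, or 13.0 weeks. Taking the start anywhere from 22 to 31 May gives 12.3 to 13.6 weeks.
- Earliest last dose, 27 September 2023, to 31 July 2024: 308 days, or 44.0 weeks.

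**Earlier challenges, in weeks of treatment**

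- Year 1: (365 − 180)/7 = 26.4 to (365 − 28)/7 = 48.1.
- Year 2: (730 − 180)/7 = 78.6 to (730 − 28)/7 = 100.3.

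**Skin prick titration.** This is done at S15, at least 28 days after S14, so its earliest nominal interval is 188 + 28 = 216 days (30.9 weeks). It can reach a year: 26 February 2024 to 28 February 2025 is 368 days.

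**The case against.** The strongest defence is that the anchor is deliberate. Appendix 5 gives the reason, and the baseline NAC is the model covariate, so keeping later challenges at the same time of year is sensible. With a gap of at least 28 days, calendar matching and a full year off treatment cannot both hold nominally. This stands as a reason for the schedule. It does not make the one-year label accurate.

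The 27-week end is also an extreme, needing a 1 September challenge and an end-of-February first dose. That is fair. The documents do not give the actual distribution, which is why it should be tabulated.

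Some readers might go further than the documents allow:

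- **That nobody can be a year off treatment.** Table 7 lets visits move for pollen count and availability without a stated limit, Section 3.1 has the looser anchor, and participants who stop treatment early are invited to stay for assessments (Sections 6.5 and 11.4). Some may pass one year. The finding concerns those treated on schedule.
- **That the shorter interval biases the comparison towards the combination arm.** All three arms follow one schedule under double-blind randomisation. The year-3 contrast is a valid comparison at the interval observed.
- **That the season starts in mid-May.** That date comes from a footnote to Appendix 1, which covers the baseline year. The SAP's description for all study years is about the end of May.
- **That a subset with long time off treatment would rescue the claim.** Actual weeks off treatment is a post-randomisation variable. Selecting on it, or using it as a modifier, favours early discontinuers and loses the protection of randomisation.

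**Conclusion.** The point holds. The documents give the year-3 NAC a property, one year off treatment, that Table 7 and Appendix 5 do not deliver for participants who complete 104 weeks on schedule. The interval is nominally 188 to 340 days (about 27 to 49 weeks), or about 23 to 52 weeks with the tolerances. The 2024 in-season endpoints fall roughly 13 to 44 weeks after the last dose. Skin prick titration at S15 is less affected. The year-1 and year-2 challenges fall at about weeks 26 to 48 and 79 to 100 of treatment. Section 3.1 adds a conflicting anchor, under which one year is reached only rarely.

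These figures assume dosing on schedule, a baseline NAC between September 2021 and January 2022, and visits inside the stated windows. The randomised contrast is not biased. The consequence is for the meaning of the endpoint and for the tolerance claim.

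**What to change.** 1. Reconcile Protocol Sections 3.1 to 3.3 and SAP Section 9.1 with Table 7 and Appendix 5, including the two NAC anchors. Describe the primary endpoint as the NAC 3 calendar years after the baseline NAC, nominally about 27 to 49 weeks (23 to 52 with tolerances) after scheduled end of treatment.
2. In the SAP, derive actual weeks from last dose to S14 and to the 2024 season, and tabulate them by arm.
3. Limit the tolerance claim to the interval observed.
4. If effect modification is explored, use the Visit -1 to Visit 0 gap, which is fixed at randomisation, as the modifier in a supportive model. Do not use a subset defined by time off treatment, or an interaction with actual weeks off treatment.

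The note at the end of the SAP shows that the plan was final and the database locked, so any added analysis must be labelled post hoc. The cost is endpoint wording, a few derived variables from dates already recorded (SAP Sections 6.1 and 7.3), one table and at most one supportive model. The downside is a less favourable label for the claim.
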